 - Patients can be consented but not randomized before the first troponin test result is available. Patients whose initial troponin level is markedly elevated will not be randomized and will not be included in the intent-to-treat population. Patients whose subsequent troponin testing is markedly elevated will be included in the intent to treat population.
 - Removed the phrase, ‘based upon blocked assignment in groups of 30’ from the end of the sentence: ‘Study subjects will be randomized into the standard care arm or the intervention arm by means randomization stratified by institution and gender using a central computerized randomization system.’
3. Clarification of the Statistical Considerations section (pages 5, 18, 24, 27-28).
 - Removed sentence, ‘Length of hospital stay between study arms will be compared in subgroups of patients directly discharged from the ED and patients admitted to the hospital.’ from primary endpoint analysis.
 - Minor clarification to emergency department triage accuracy assumption discussion.
 - Minor clarification to secondary aim of health care utilization.
 - Removed sentence, ‘We will use an uncorrected chi-squared statistic to evaluate this null hypothesis.’ from discussion of secondary aim for comparison between two groups of rate of MACE at 1 and 2 years.

Amendment 2 Summary of Changes

1. Changes to Inclusion/Exclusion Criteria (page 20):

- Page 20: The baseline population of ROMICAT I (age >40) had an ACS rate of 9.3%. For subjects with ≥ 1 risk factor, the ACS rate rose to 10.0% at the cost of losing 17% of the population, while for subjects with ≥ 2 risk factors, the ACS rate rose to 13.9% with a loss of 46% eligible subjects. As the role of risk factors in determination of ACS is controversial, and based on DSMB recommendations, this criterion will be removed from the inclusion criteria.
- Page 21: The exclusion criteria of subjects who present to the ED more than 4 hours ago will now be extended to more than 6 hours ago. This is based on DSMB recommendations as a useful technique to capture subjects who present with chest pain early in the morning.

2. Clarification of Study Protocol

- Pages 31, 43: Currently the CT protocol only covers retrospective gating. This will be amended to extend to allow prospective triggering also, as this is a pragmatic trial which should reflect current clinical practice. This also has the potential benefit of reduced radiation exposure (<5mSv).
- Page 24: Subjects discharged within 24 hours of presentation to the hospital will be followed up at the 48-72 hour period. This was mentioned as 48 hours in the protocol, and was a typographical error.
- Page 25: We will remove all language suggestive of facilitated handling of patients in the CT arm (including scheduling the CT scan immediately after randomization, and notification of the ED caregivers about the results of the CT scan in a given time frame). The sentences "To facilitate timely CT imaging, the cardiac CT exam will be scheduled immediately after randomization", "The results of cardiac CT including the presence and extent of coronary atherosclerotic plaque, coronary artery stenosis, and global and regional LV dysfunction will be provided to the ED caregivers immediately" and "In subjects randomized to receive a cardiac CT, patient management will be additionally informed and guided by the cardiac CT findings on coronary plaque and stenosis and LV function. CT will be discussed with the ED physicians caring for the subject." have been removed from page 23. "The CT reader will contact the Emergency Department (ED) treating physician and report the results of the cardiac CT" has been removed from page 49 of Appendix B.
- Page 24: Gender stratification will not be used in the randomization schema for the simplicity, and to use it as a covariate in further statistical analysis.

- Page 33: MD over read will be performed for internal quality control assessment of findings related to CAD and significant cardiac findings such as pulmonary embolism and aortic dissection, to increase awareness to sites of non-coronary findings.

3. Clarification of Aims

- Page 18: The language of the aims and related hypotheses has been expressed in a more clarified manner.

Amendment 3 Summary of Changes

1. Changes to Inclusion/Exclusion Criteria (page 25):

- Page 25: Participant must have at least five minutes of chest pain or equivalent (chest tightness; pain radiating to left, right, or both arms or shoulders, back, neck, epigastrium, jaw/throat; or unexplained shortness of breath, syncope/presyncope, generalized weakness, nausea, or vomiting thought to be of cardiac origin) at rest or during exercise within 24 hours of ED presentation, warranting further ~~inpatient~~ risk stratification, as determined by an ED attending.
- Page 26:
 - 9. Currently symptomatic asthma (~~or taking daily medication for asthma~~)
 - 10. Contraindication to beta blockers (**taking daily antiasthmatic medication**):
This exclusion only applies to patients with a heart rate > 65 bpm at sites using a non-dual source CT scanner

2. Clarification of Study Protocol:

- Page 28: *Interventional Arm*: In subjects randomized to the intervention arm, a contrast enhanced cardiac CT will be performed (after initial troponin level is available) in addition to the ~~standard evaluation~~ **initial ED evaluation**.

3. Extension of follow-up time windows:

- Page 28: The 48-72 hour follow-up phone call has been extended to accommodate calls that fall either during the weekend or during a holiday.
- Page 29: The 12 month and 24 month follow-up phone call windows have been extended from +/- 2 weeks to +/- 4 weeks.

Amendment 4 Summary of Changes

1. Study Synopsis (page 13):

Duration of Study Participation: Participants will be followed during index ED visit/hospitalization. There will be a phone call at 48-72 hours for those discharged within 24 hours. All participants will receive a follow up phone call at 28 days, ~~1-year and 2-year~~ post emergency room discharge.

2. Changes to Inclusion Criteria (page 27):

- Participant must be in ~~normal~~ sinus rhythm.

3. Elimination of the 1 and 2 year follow-up interviews:

- Page 16: All participants will receive a 28-day, ~~a one year and two year~~ follow-up phone interview. The efficiency of each strategy will be determined by comparing 1) the length of hospital stay (primary endpoint), 2) the time to diagnosis (secondary endpoint), 3) the rates of ED discharge (secondary endpoint), 4) utilization of other diagnostic testing, i.e. invasive coronary angiograms, and resulting interventions, i.e. coronary revascularization procedures during index hospitalization **and** 28 days, ~~one year and two year~~ (secondary endpoint). The safety of the two strategies will be compared by determining the occurrence of adverse events within 48-72 hours in directly discharged patients as well as determination of major adverse cardiovascular events (MACE) within 28 days, ~~one year and two years~~ after discharge from the index hospitalization.
- Page 26: ~~To compare the two study arms in terms of rates of MACE (major adverse cardiac events—cardiac death, AMI, revascularization, unstable angina, and rehospitalization) within one and two years.~~

~~**One/two Years:** Defined as one/two years post the day of discharge from index hospitalization.~~

~~Hypothesis: *The rates of MACE in both arms during the follow up period will be lower in the CT arm.*~~

- Page 30: A reminder letter will be sent or phone call will be made to participants, two weeks prior to the 28-day follow up phone call. **If unable to contact the participant by phone, mortality will be assessed online using the SSDI website.**
- Page 30: ***5.4 12 Month Follow up***
~~*Follow up one year phone call:* All subjects will be interviewed via a telephone call at one year post ED discharge (12 months +/- 4 weeks) to determine the occurrence of MACE and readmissions to the hospital using a standardized questionnaire. All cases of recurrent chest pain, hospital admissions, and diagnostic testing will be verified by review of medical records.~~

~~A reminder letter will be sent or phone call will be made to participants, two weeks prior to the 12-month follow-up phone call.~~

~~5.5 24 Month Follow-up~~

~~*Follow-up two-year phone call:* All subjects will be interviewed via a telephone call at two years post-ED discharge (24 months +/- 4 weeks) to determine the occurrence of MACE using a standardized questionnaire. All cases of hospital admissions and diagnostic testing will be verified by review of medical records.~~

~~Note: A reminder letter will be sent or phone call will be made to participants two weeks prior to the two-year follow-up phone call. A minimum of five (5) phone attempts will be to contact each participant. If unable to contact the participant by phone, mortality will be assessed online using the SSDI website.~~

- ~~• Page 34: *To compare the two study arms in terms of rates of MACE (cardiac death, AMI, revascularization, unstable angina, and rehospitalization) within one and two years.*~~

~~This analysis will be performed from the intent to treat perspective. The occurrence of MACE will be assessed via patient follow-up and medical chart review. The primary analysis for this aim will be performed at the patient level by determining whether any MACE occurred or not. Event rates will be estimated and compared between study groups using exact procedures. Prior data estimate a MACE rate of 5% over two years. We anticipate a MACE rate between 2% and 5% in both groups and have 80% power to detect a difference between 2 and 5% between the two groups. The Type I error probability associated with this test of this null hypothesis is 0.05.~~

~~In a secondary analysis, the rates of each type of MACE will be examined separately.~~

4. Extension of 28-Day follow-up time window:

- Page 30: The 28-day follow-up phone call window has been extended from +2 weeks to +4 weeks.

Amendment 5 Summary of Changes

1. Study Synopsis (page 15):
Number of sites: 9 ~~7~~

2. Part I: Study Overview (page 17):
The study is designed as a randomized, controlled, diagnostic, multicenter trial and will enroll 1,000 participants at nine ~~seven~~ sites over a 15 month period.

3. Study Design (page 18):
The study is designed as a randomized, controlled, diagnostic, multicenter trial and will enroll 1,000 participants at nine ~~seven~~ sites over a 15 month period.

Study Synopsis

Sponsor(s)	National Heart Lung and Blood Institute (NHLBI)
Protocol Title	R ule O t M yocardial I schemia/ I nfarction U sing C omputer A ssisted T omography - A Diagnostic Randomized Multicenter Trial
Diagnosis and Main Criterion for Inclusion	Adults (≥ 40 -75 yrs) without known/documentated history of coronary artery disease, who have come to the emergency department (ED) presenting with a lead symptom of acute chest pain suggestive of acute cardiac ischemia, defined as chest pain lasting for at least 5 minutes, and occurring within the last 24 hours but without diagnostic ECG changes of acute myocardial ischemia are eligible for participation. Only patients in whom the ED attending feels that further inpatient risk stratification is required will be included.
Primary Study Objective	To determine whether length of hospital stay is significantly shortened in the interventional arm vs. standard of care
Secondary Study Objectives	
 • To determine whether time to diagnosis (for ACS and no ACS) is significantly shortened and rates of direct discharge from the emergency department are increased in the interventional arm vs. standard of care • To determine a) the additional number of invasive coronary angiograms in both arms and b) to determine the number of coronary revascularization procedures. • To determine the safety of immediate ED discharge after a normal cardiac CT defined as the occurrence of ACS within 48-72 hours after discharge. • To determine whether subsequent testing and follow-up, including invasive coronary angiograms, diagnostic (imaging) tests, interventions, repeat ED visits for cardiac related problems and repeat hospitalizations for chest pain or equivalent during 28 days after hospital discharge is decreased in the interventional arm, compared to SOC. • To determine the two study arms in terms of rates of MACE within 28 days. • To compare the two study arms in terms of rates of MACE within one and two years. • To estimate and compare the sensitivity, specificity, NPV and PPV of contrast-enhanced CT and non-contrast CT, with clinical diagnosis of ACS as the reference standard. • To determine whether the cost of care (per TSI) for index hospitalization and after 28 days is decreased by implementing cardiac CT into the early ED evaluation of patients with acute chest pain. • To determine the cost-effectiveness of incorporating cardiac CT into

	the standard ED evaluation of patients with acute chest pain over a 28-day and lifetime horizon as compared to SOC.
Tertiary Study Objectives	
 • To determine whether CT leads to increased test burden after the initial tests during index hospitalization. • To compare the consistency of physician decisions management depending on the results of diagnostic testing (i.e. normal CT – what fraction is immediately discharged) • To determine whether hospital setting, availability of observation unit, CT experience of hospital and readers, and reader performance are associated with primary or secondary outcomes.
Primary Endpoint	The primary endpoint is time from ED presentation to hospital discharge. The length of hospital stay is defined as the time from ED presentation to the time of discharge note or order. This includes time in the ED, time in any institution-specific specialized chest pain unit, and time as an inpatient on the floor
Secondary Endpoints	
 • The time to diagnosis: For ACS, defined as the time from ED presentation until the first test during index hospitalization that leads to the diagnosis of ACS (tests may be biomarkers, CTA, ETT, nuclear imaging, stress ECHO or cardiac catheterization); for no ACS, defined as the time from ED presentation to the final test during index hospitalization. • Admission to hospital: Participants are considered to be admitted if the ED attending admitted the subject to a hospital floor (medical floor, step down unit, telemetry hospital floor or intensive care unit). • Direct ED discharge: will include all subjects who are not admitted to the hospital. • Health care utilization: number of invasive coronary angiograms, diagnostic (imaging) tests, interventions, repeat ED visits. • Rates of MACE: major adverse cardiac events – cardiac death, acute myocardial infarction, revascularization, unstable angina and rehospitalization. • Cost of care derived from the cost-accounting database (i.e., TSI).
Tertiary Endpoints	Increased test burden: Further imaging tests performed after index hospitalization
Primary Hypothesis	Adding cardiac CT to the initial ED evaluation of subjects with acute chest pain significantly decreases length of hospital stay.

Secondary Hypothesis	Addition of cardiac CT to the initial ED evaluation of subjects with acute chest pain will significantly increase the ED discharge rate, and shorten the time to diagnosis and it will be a cost-saving and cost-effective modality. There will not be an increase in the number of invasive angiograms or coronary revascularization procedures as compared to the SOC arm. With a high negative predictive value, patient safety will not be compromised. There will not be an increase in subsequent further testing and the rate of MACE in both arms in the follow-up period will be similar. The test characteristics of contrast enhanced CT will be significantly better than that of a non-contrast CT.
Study Design	The study is designed as a randomized diagnostic multicenter trial and will enroll 1,000 participants at seven sites over a 15 month period. Participants presenting with acute chest pain in the ED will be randomized to standard of care (SOC) or to an interventional arm. Patients in the interventional arm will receive standard evaluation supplemented by contrast-enhanced cardiac CT imaging
Duration of Study Participation	Participants will be followed during index ED visit/hospitalization. There will be a phone call at 48-72 hours for those discharged within 24 hours. All participants will receive a follow up phone call at 28 days post emergency room discharge.
Number of Subjects	1,000 subjects will be enrolled, with 500 each in the standard of care and interventional arms.
Number of Sites	9
Statistical Considerations	The primary aim of the study is to compare the two study arms in terms of a difference in mean length of hospital stay (LOS) between the two arms. We have conducted a power evaluation using the estimated mean and standard deviation based on observed data from ROMICAT I and simulated data based on health outcomes. We will have 95% power to detect a difference in 10 hours of LOS at a Type-1 error rate of 5% for an independent samples t-test using 500 patients in each arm.

Part I: Study Overview

The study is designed as a randomized, controlled, diagnostic, multicenter trial and will enroll 1,000 participants at nine sites over a 15 month period. Participants presenting with acute chest pain in the ED will be randomized to a standard of care arm (SOC) or interventional arm; patients in the interventional arm will receive standard evaluation supplemented by contrast-enhanced cardiac computed tomography (CT) imaging (Figure 1).

In both arms, the initial Emergency Department (ED) evaluation (electrocardiogram [ECG], physical examination, clinical presentation, renal function lab, and medical history) will determine eligibility of patients. After randomization, standard of care will be performed in both arms. However, for patients randomized to the interventional arm, a CT will be performed. The following decisions made by the caregiver team will be tracked: admission or discharge after initial ED evaluation plus CT/other initial diagnostic test, in admitted participants, the length of hospital stay, the extent of further testing including serial cardiac markers and ECG, and other diagnostic tests or interventions. For safety reasons, participants discharged in less than 24 hours of ED arrival will receive a phone call 48-72 hours after discharge. All participants will receive a 28-day follow-up phone interview. The efficiency of each strategy will be determined by comparing 1) the length of hospital stay (primary endpoint), 2) the time to diagnosis (secondary endpoint), 3) the rates of ED discharge (secondary endpoint), 4) utilization of other diagnostic testing, i.e. invasive coronary angiograms, and resulting interventions, i.e. coronary revascularization procedures during index hospitalization and 28 days (secondary endpoint). The safety of the two strategies will be compared by determining the occurrence of adverse events within 48-72 hours in directly discharged patients as well as determination of major adverse cardiovascular events (MACE) within 28 days after discharge from the index hospitalization. We will also perform a cost and cost effectiveness analysis. In subsequent analyses, we will determine the patient, physician, and institutional factors that affect the primary endpoint or secondary endpoints.

Primary Objective:

To determine whether length of hospital stay is significantly shortened in the interventional arm vs. SOC.

Hypothesis:

Adding cardiac CT to the initial ED evaluation of subjects with acute chest pain decreases length of hospital stay.

Part II: Study Description

1. Background and Significance

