3.2 Secondary Aims

1. To determine whether time to diagnosis is significantly shortened and rates of direct discharge from ED are increased in the interventional arm vs. SOC.

A) Time to Diagnosis:

For **ACS**: Defined as the time from ED presentation until the first test during index hospitalization that leads to the diagnosis of ACS (tests may be biomarkers, CTA, ETT, nuclear imaging, stress ECHO or cardiac catheterization), For no ACS: Defined as the time from ED presentation defined as the final test during index hospitalization.

B) Admission to Hospital: Participants are considered to be admitted if the ED attending admitted the subject to a hospital floor (medical floor, step down unit, telemetry hospital floor, or intensive care unit)

Direct ED Discharge will include all subjects who are not included in (B).

Hypothesis: *ED evaluation of subjects with acute chest pain supplemented by cardiac CT significantly increases direct ED discharge rates and shortens time to diagnosis for both ACS positive and negative patients.*

2. To determine a) the additional number of invasive coronary angiograms, both arms, and b) to determine the number of coronary revascularization procedures.

Hypothesis: *ED evaluation of subjects with acute chest pain supplemented by cardiac CT will not increase the number of invasive coronary angiograms without revascularization or revascularizations during index hospitalization.*

3. To determine the safety of immediate ED discharge after a normal cardiac CT defined as the occurrence of ACS within 48-72 hours after discharge.

Hypothesis: *CTA has a high negative predictive value based on which immediate ED discharge should not compromise patient safety.*

4. To determine whether subsequent testing and follow up, including invasive coronary angiograms, diagnostic (imaging) tests, interventions, repeat ED visits for cardiac related problems, and repeat hospitalizations for chest pain or equivalent during 28 days after hospital discharge is decreased in the interventional arm compared to SOC,.

Hypothesis: *Incorporation of CTA in the evaluation of acute chest pain patients in the ED will not lead to decreased further testing to manage chest pain when as compared to the SOC arm.*

5. To compare the two study arms in terms of rates of MACE (major adverse cardiac events—cardiac death, AMI, revascularization, unstable angina, and rehospitalization) within 28 days.

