3.3 Tertiary Aims

1. To determine whether CT leads to increased test burden after the initial tests during index hospitalization.

Hypothesis: *Cardiac CT may diagnose coronary artery disease at a more incipient stage than determined by imaging tests in the SOC arm, which may increase test burden during the follow up period.*

2. Compare the consistency of physician decisions management depending on the results of diagnostic testing (i.e. normal CT - what fraction is immediately discharged)

Hypothesis: *There will be comparable consistency between the two arms.*

3. Determine whether hospital setting, availability of Observation Unit, CT experience of hospital and readers, and reader performance are associated with primary or secondary outcomes.

Hypothesis: *Enhanced CT experience of the hospital and readers, better reader performance during CT certification and hospital setting will be associated with improved primary or secondary outcomes.*

4. Participant Selection/Eligibility Criteria

Adult ED participants presenting with a lead symptom of acute chest pain suggestive of acute cardiac ischemia - defined as chest pain lasting for at least 5 minutes and occurring within the last 24 hours but without diagnostic ECG changes of acute myocardial ischemia - will be eligible for participation.

Only patients in whom the ED attending feels that further inpatient testing is required will be included. Patients with known/documented history of CAD will not be included since such patients most often have an abnormal or non-diagnostic cardiac CT. In addition, men and women younger than 40 years will be excluded due to the low pre-test likelihood for CAD and the increased radiation risk. Detailed inclusion and exclusion criteria are presented below.

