of discharge rates we will have a 100% chance at a significance level of 0.05 to detect a 17% increase in discharge rates from 15% to 32%.

The comparison of time to discharge among patients who are admitted to the hospital is complicated by the fact that the two groups will not be the same group of patients. For instance, patients who would have been discharged in the cardiac CT group but admitted in the usual care group may have a relatively shorter time post admission than patients who would have been admitted in both groups. We have developed methods for analyzing these types of data using causal inference that will be applied to this analysis.⁶¹ A similar analysis will be applied to other subgroups such as those with and without ACS.

To compare the two study arms in terms of cardiac health care utilization during the index visit. Health care utilization components will include invasive coronary angiograms and coronary revascularization..

The analysis for this secondary aim will be performed from the intent to treat perspective. Health care utilization will be assessed using medical record review. Measures of key components of utilization will be compared across the two study groups using procedures appropriate for each measure (rate or count).

In particular the two arms will be compared in terms of the number of invasive coronary angiograms. This secondary endpoint will be analyzed in terms of a non-inferiority trial. In a non-inferiority trial the null hypothesis is that cardiac CT is worse than usual care in that the rate of coronary angiograms is increased and the alternative hypothesis is that it is not in worse and the rate of angiograms is the same. The reason for reversing the usual null and alternative hypothesis is that the purpose of this analysis is to prove that cardiac CT is not worse than usual care, this would not be accomplished by just showing that the difference between the two was not significant.

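### Direct ED discharge is defined as not being admitted to a hospital floor, so read literally it counts patients held in a chest-pain or observation unit as discharged directly from the ED

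*Protocol*

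**What the plan says.** The Protocol classifies disposition by a rule and its complement. In the Study Synopsis (Secondary Endpoints), "Participants are considered to be admitted if the ED attending admitted the subject to a hospital floor". The bracketed list that follows names a medical floor, a step-down unit, a telemetry floor and intensive care. Everyone else falls into the other category: "Direct ED discharge: will include all subjects who are not admitted to the hospital". Section 3.2, aim 1, repeats both parts.

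The primary endpoint works with three locations, not two. The Synopsis (Primary Endpoint) says of length of stay: "This includes time in the ED, time in any institution-specific specialized chest pain unit, and time as an inpatient on the floor". Section 3.1 uses the same definition. Section 3.3, aim 3, asks whether "availability of Observation Unit, CT experience of hospital and readers, and reader performance are associated with primary or secondary outcomes", so units are expected at some sites and not at others.

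The planning text in Section 7.2 has only two categories. In standard care 15% are discharged and 85% admitted. The CT rate of 32% comes only from patients without CAD on CT who are then discharged directly from the ED. Section 7.2 concludes that "we will have a 100% chance at a significance level of 0.05 to detect a 17% increase", from 15% to 32%.

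**The concern.** No passage places a chest-pain or observation unit among the admitting locations. Because discharge is whatever is left over, a patient held overnight in a unit for serial markers and a stress test is counted with patients sent home from the ED. The aim is to show that CT lets more patients leave directly from the ED, and a rule that counts unit stays as successes measures something else.

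Three things are at stake. The reported rates would depend on which sites have a unit. The difference between arms would no longer be the one that was planned for. The same classification also defines the admitted patients whose time to discharge is compared in Section 7.2, the discharge rate used in the interaction tests for sex and minority status (Section 7.3), and the group in which missed ACS is considered (Sections 7.2 and 11).

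**Working it through.** **Inputs from the Protocol.** 500 patients per arm (Synopsis); 15% in standard care and 32% in the CT arm, significance level 0.05, stated power 100% (Section 7.2). Sidedness is not stated; two-sided is used here.

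**The 32%.** Section 7.2 expects 40% to 50% without CAD, of whom 60% to 80% are discharged. 0.40 × 0.60 = 0.24 and 0.50 × 0.80 = 0.40; the midpoint is 0.32. Unit stays do not enter this calculation.

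**The stated power.** With p̄ the mean of the two rates,

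power = Φ{ [d − 1.96·√(2p̄(1−p̄)/n)] / √[(p₁(1−p₁) + p₂(1−p₂))/n] }.

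For 0.15 and 0.32: d = 0.17 and p̄ = 0.235. The numerator is 0.17 − 1.96 × 0.02682 = 0.1174 and the denominator is √(0.3451/500) = 0.02627. The ratio is 4.47 and power is 0.999996. A one-sided test gives 0.999999. The stated 100% reproduces.

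**Effect of the literal rule, equal unit use.** Two assumptions are needed. First, the 15% and 32% exclude unit stays. Second, a share o of the patients not sent home from the ED goes to a unit, the same in both arms. The Protocol gives no value for o, so a range is shown. Under the literal rule:

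- standard care: 0.15 + 0.85o
- CT: 0.32 + 0.68o
- difference: 0.17(1 − o)

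| o | Standard care | CT | Difference (points) | Power |
|---|---|---|---|---|
| 0% | 15.0% | 32.0% | 17.0 | >99.99% |
| 20% | 32.0% | 45.6% | 13.6 | 99.3% |
| 30% | 40.5% | 52.4% | 11.9 | 96.6% |
| 40% | 49.0% | 59.2% | 10.2 | 90.0% |
| 50% | 57.5% | 66.0% | 8.5 | 79.1% |
| 60% | 66.0% | 72.8% | 6.8 | 64.6% |

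**Unequal unit use.** CT may change who is sent to a unit, so the shares need not agree.

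- 30% in standard care and 20% in the CT arm: 0.15 + 0.85 × 0.30 = 40.5% against 0.32 + 0.68 × 0.20 = 45.6%. The difference is 5.1 points and power is about 37%.
- 30% and 10%: 40.5% against 0.32 + 0.68 × 0.10 = 38.8%, a reversal of 1.7 points.
- With 30% in standard care, the sign changes once the CT share falls below (0.405 − 0.32)/0.68 = 12.5%.

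In the last two cases the CT arm sends 17 points more patients home and still shows no advantage on the endpoint as defined.

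**The case against.** The strongest reply is that the planning figures may already follow the endpoint rule. The 15% comes from a site survey and published data, and Section 7.2 does not say how unit stays were classed. If they were already counted as discharges, adding 0.85o counts them twice. This stands: a reader might infer that the definition invalidates the 15% versus 32% power statement, and the Protocol does not support that. The reply does not rescue the 32%, which is built from direct discharges after a CT without CAD. If only the 15% includes unit stays, the two rates rest on different rules.

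A second reply is that the text is ambiguous, not wrong. Section 1.4 links observation units to a lower threshold for admitting patients, and Section 5.1 describes the admitted patient's course as observation and monitoring. Both suggest that a unit stay was thought of as admission. That is a fair reading of intent, but the operative definition, given twice, says otherwise.

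Third, some protection exists. Unit time counts toward the primary endpoint, randomization is stratified by institution (Section 4.4), and Section 3.3 examines unit availability. These points stand against a charge of confounding by site. They do not change what the secondary endpoint measures.

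A reader might also infer that the misclassified patients sit mostly in standard care, so that the effect can only shrink. With equal shares the standard-care part is 0.85/(0.85 + 0.68) = 56%, a slight majority, and with unequal shares the direction is open. Transfers and deaths in the ED also fall into the residual category, but they are a minor matter.

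**Conclusion.** The point holds as a mismatch between a stated definition and the aim it serves. Taken literally, the rule counts chest-pain and observation unit stays as direct ED discharges. This disagrees with the stated aim and with the derivation of the 32%, and it ties the rate to local facilities.

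Its size cannot be fixed from the Protocol because no unit share is given. If the planning rates exclude unit stays and unit use is equal between arms, power stays at 90% or more up to a share of about 40% and is 79% at 50%. If unit use differs between arms, the difference may shrink sharply or reverse. Even where power holds, the reported rates would not answer the question asked.

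The Protocol ranks this as a secondary endpoint, and the primary endpoint, its analysis and the sample size are untouched. It is a moderate correction.

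**What to change.** In the Synopsis (Secondary Endpoints) and Section 3.2, aim 1, define direct ED discharge as discharge home from the ED without transfer to a hospital floor or to a chest-pain or observation unit. Record disposition in four categories: home from the ED, observation or chest-pain unit, hospital floor, other. Report unit stays as their own category by arm.

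In Section 7.2, state whether the 15% and the 32% both follow this definition. If they do, the power statement stands at about 100%. If they do not, restate the rates and the power.

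The cost is one definition, changed in two places, and one disposition field. Section 3.1 already requires all time sequences that make up length of stay, including unit time, to be documented.
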